If the rate of missing data for the endpoint is imbalanced between treatment groups (demonstrated by Fisher's exact test with a p-value of <0.05) and the rate of missing data for the endpoint is greater than 5% in all subjects, then the primary analyses will utilize the ITT population with observed data only using the permutation test with trimmed means methodology with Estimand 2:

Estimand 2:

- Population:
 - ITT population
- Endpoint:
 - Change from baseline [REDACTED] in total corneal fluorescein staining score in the study eye at Day 29 [REDACTED] in the ITT population
- Intercurrent event:
 - Discontinuation of study medications is ignored. Measures obtained after discontinuation of study medication will be analyzed. [treatment policy strategy]
 - Non-optimal compliance is ignored. Measures will be analyzed regardless of treatment compliance. [treatment policy strategy]

- Use of prohibited concomitant medications is ignored. Measures obtained after use of prohibited concomitant medications will be analyzed. [treatment policy strategy]
- Withdrawal or missed assessments for any reason. Missing values will be trimmed from analyses in accordance to trimmed means methodology. [hypothetical strategy]
- Population-level summary:
 - Difference in the mean change from baseline [REDACTED] in total corneal fluorescein staining score in the study eye at Day 29 [REDACTED] between 0.3% SI-614 and placebo in the ITT population.

Analyses using the ITT population with multiple imputation with Estimand 1 will be additional sensitivity analyses.

The proportion of data trimmed in the permutation test with trimmed means analysis will be dependent on the maximum rate of missing data in any treatment group using the following:

Maximum Rate of Missing Data (%)	Data Trimmed (%)
>5% to <10%	10%
10% to <20%	20%
20% to <30%	30%

In the event that the maximum rate of missing data exceeds 30% in any treatment group, then the percentage trimmed will increase by a decile until the percentage trimmed exceeds the maximum rate of missing data in any treatment group.

The ANCOVA model used to compare the change from baseline [REDACTED] to Day 29 [REDACTED] in corneal total fluorescein staining score in the study eye between 0.3% SI-614 and placebo will include baseline [REDACTED] in corneal total fluorescein staining score in the study eye at Visit 2 and treatment group as covariates.

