4.1.1 STATISTICAL HYPOTHESES OF PRIMARY ENDPOINT

The statistical hypotheses are stated in terms of one-sided hypotheses, at a significance level of 0.025.

H_{01} : The change from baseline Visit 2 (Day 1, [REDACTED] to Visit 5 (Day 29, [REDACTED] in tCFS score [REDACTED] of the study eye for 0.3% SI-614 is equal or greater than placebo.

H_{A1} : The CFB Visit 2 (Day 1, [REDACTED] to Visit 5 (Day 29, [REDACTED] in tCFS score [REDACTED] [REDACTED] of the study eye for 0.3% SI-614 is less than placebo.

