- **Estimand 2:** If the rate of intercurrent events such as lack of efficacy or AEs for the endpoint is imbalanced between treatment groups (demonstrated by Fisher's exact test with a p-value of <0.05) and the rate of intercurrent events for the endpoint is greater than 5% in all patients, then the primary analyses will utilize ITT population with Estimand 2. The trimmed mean approach will be applied to the primary analyses. The patients' data, missing or non-missing, will be trimmed if the patients experience the intercurrent events such as treatment discontinuation due to lack of efficacy or treatment discontinuation due to AEs. The permutation test will be used to test the treatment difference. The trimmed proportion is as shown on Table 2.

Table 2. Proportions of Data Trimmed

Maximum Rate of intercurrent events in any treatment group (%)	Data Trimmed (%)
5% to <10%	10%
10% to <20%	20%
20% to <30%	30%

The following intercurrent events will be considered in Estimand 2:

- Treatment discontinuation due to lack of efficacy or AEs before the assessment of the primary endpoint – will be trimmed irrespective of missingness or not
- Missing data as results of treatment discontinuation due to reasons other than lack of efficacy or AEs, assumed to be MAR, will be multiply imputed using randomized treatment group-based MCMC imputation. [hypothetical strategy]
- Non-optimal compliance is ignored. Measures will be analyzed regardless of treatment compliance [treatment policy strategy], assuming the non-compliance is not associated with the assigned treatments.
- Use of prohibited concomitant medications is ignored. Measures obtained after use of prohibited concomitant medications will be analyzed [treatment policy strategy]
- Subjects who were mis-randomized will be analyzed as randomized using the correct baseline information.

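### If Estimand 2 is triggered, its trimmed-mean permutation test judges discontinuation and staining together (on the natural reading of the trimming rule), while H01 and the success rule concern staining alone

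*SAP*

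**What the plan says.** **Hypothesis.** SAP 4.1.1: "The statistical hypotheses are stated in terms of one-sided hypotheses, at a significance level of 0.025". H01 is that the tCFS change to Day 29 "of the study eye for 0.3% SI-614 is equal or greater than placebo". Discontinuation is not mentioned. SAP 9.5 declares success and opens the secondary test if this endpoint is significant.

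**Trigger.** SAP 4.1.2 sets two conditions for Estimand 2. One is that event rates are "imbalanced between treatment groups (demonstrated by Fisher's exact test with a p-value of <0.05"); the other is an overall event rate above 5%.

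**Test.** Discontinuations for lack of efficacy or an adverse event before the primary assessment "will be trimmed irrespective of missingness or not". Table 2 sets the fraction (10%, 20% or 30%) from the higher arm-specific event rate. Then: "The permutation test will be used to test the treatment difference". The SAP does not say which observed scores, if any, complete the fraction. It gives the trimmed event no strategy label and gives Estimand 2 no population-level summary.

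**Elsewhere.** SAP 14.1.1 names an ANCOVA for the primary analysis under either estimand. SAP 21 says Estimand 1 tables are not produced if Estimand 2 is used. Protocol 11.4.4 describes its Estimand 2 differently: "Missing values will be trimmed from analyses in accordance to trimmed means methodology. [hypothetical strategy"], with the summary beginning "Difference in the mean change from baseline". It also keeps Estimand 1 as a sensitivity analysis in that case.

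**The concern.** A label-permutation test builds its reference distribution on the premise that everything entering the statistic is exchangeable between arms. Here that includes who discontinued as well as the staining scores. With a common trimming fraction, the arm with fewer discontinuations must fill its quota from observed scores. If those are its worst scores, its trimmed mean improves for a reason unrelated to any drug effect on staining.

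The test becomes primary only after a significant imbalance in discontinuation, which is where the joint question and the staining question are most likely to differ. The SAP's own Estimand 1 notes expect more lack-of-efficacy exits on placebo and more adverse-event exits on active treatment, so the distortion could run either way. At stake is a success declaration on staining, and the opening of the secondary test, that discontinuation alone could produce or prevent.

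**Working it through.** **1. The plan's own figure.** Protocol 11.3 gives difference -0.75, SD 1.7, two-sided 0.05 and 90% power. n = 2(1.7/0.75)²(1.960+1.282)² = 108 per arm by the normal formula and 108.94, so 109, by the t version. 109/0.95 = 114.7, so 115. The stated 109 and 115 reproduce.

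**2. What triggers Estimand 2 at 115 per arm.** The overall rate must exceed 5% of 230, so at least 12 events. For example, 2 v 10 qualifies (12/230 = 5.2%, Fisher p = 0.034). Exact binomial probabilities of triggering, for assumed true event rates in the two arms:

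| True rates | P(trigger) |
|---|---|
| 2.5% / 2.5% | 0.04% |
| 5% / 5% | 1.2% |
| 10% / 10% | 2.8% |
| 2% / 5% | 2.8% |
| 2.5% / 7.5% | 18% |
| 4% / 12% | 51% |
| 2% / 12% | 76% |

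**3. The mechanism by hand.** Take 2 events on SI-614, 10 on placebo, no staining effect and discontinuation unrelated to staining. The higher rate is 10/115 = 8.7%, so Table 2 gives 10%: 11.5, rounded up to 12 per arm. On the worst-tail reading SI-614 also loses its 10 worst of 113 observed scores (8.8%), and placebo its 2 worst of 105 (1.9%). Cutting the top fraction p of a normal shifts its mean by -1.7φ(z)/(1-p):

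- SI-614: -1.7 × 0.160/0.912 = -0.30
- Placebo: -1.7 × 0.046/0.981 = -0.08
- Difference: about -0.22 when the truth is 0

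With the imbalance reversed, a true -0.75 becomes about -0.75 + 0.22 = -0.53.

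**4. Simulation, worst-tail reading.** Set-up: 115 per arm, normal changes with SD 1.7 rounded to integers, fixed event counts, random discontinuation, one-sided 0.025. Ranges cover repeat runs of 200 to 1,500 trials. The Monte Carlo standard error is about 1 point at 1,000 trials: √(0.12×0.88/1000).

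| Events, SI-614 v placebo | True effect | Rejects for SI-614 |
|---|---|---|
| 2 v 10 | 0 | 8-13% |
| 4 v 14 | 0 | 10-12% |
| 6 v 17 | 0 | 13-14% |
| 2 v 14 | 0 | 15-17% |
| 5 v 5; 12 v 12 | 0 | 1-2% |
| 10 v 2 | -0.75 | 52-54% |
| 14 v 4 | -0.75 | 46-51% |
| 17 v 6 | -0.75 | 37-40% |

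Equal counts show no inflation, so the imbalance is the cause. Averaging instead over all triggered trials at assumed true rates (continuous scores) gives 14.3% (2% v 8%) to 26.3% (2% v 15%) false rejection. Power is 34.2% (15% v 2%) to 50.7% (10% v 2%).

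**5. Sensitivity to the assumptions.**

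- Discontinuation correlated 0.5 with worse staining, true rates 2% and 10%: false rejection falls from 18.2% to 9.3%. With the rates reversed, power rises from 50.7% to 66.2%.
- Only event patients removed: 1.5% and 3.5% false rejection (2 v 10, 4 v 14), and 90% and 89% power reversed.
- Remaining quota taken from both tails: 1.8% and 1.8%, and 86% and 83% power.

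**The case against.** **The tail is inferred.** This is the strongest objection, and it stands as a limit on the figures. Neither document says that the worst observed scores complete the quota. Worst-tail trimming is still the natural reading, because a common fraction set at or above the larger arm's event rate has little purpose if only event patients are removed. The gap itself needs closing.

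**Fisher p<0.05 does not make the permutation null false.** A reader might infer that it does. With equal true rates Estimand 2 is still selected in about 1-3% of trials at 5-10% event rates, and the joint null then holds. Conditioning on the imbalance still matters there: 4.8% and 9.2% rejection given selection at 6% and 10% equal rates.

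**The hypothetical label and mean-change summary are protocol text.** The SAP states that its methods supersede the protocol's, and section 18 rejects the protocol's account of intercurrent events. The SAP's fault is therefore omission. Nor can one say the result would necessarily be reported as a mean difference, since protocol 11.4.4 calls for trimmed means and their differences.

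**Reach is limited.** Planned dropout is 5% for all reasons. In the 240-patient, 28-day Phase 2/3 study adverse events led 2 patients to stop. Opposing patterns of exits would partly cancel in a pooled Fisher test.

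**Some safeguards exist.** Event rates are tabulated (Table 14.1.6). The placebo-based, MCMC and observed-data ITT tables are produced under either estimand.

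**Counting discontinuation as a bad outcome is legitimate.** It is, provided the plan says so; neither document does.

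**Conclusion.** The mismatch is real but conditional. Once Estimand 2 is triggered, and if the worst tail is trimmed, the test answers a joint question about discontinuation and staining, while H01 and the success rule ask about staining only. With 115 per arm, SD 1.7 and discontinuation unrelated to staining, false rejection is about 10-15% against 2.5% when placebo has more events. Power is about 37-55% against the planned 90% when SI-614 has more.

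A reader might take these as trial-wide error rates. They are not. At 2.5% v 7.5%, with the other analyses assumed to hold 2.5%, overall false rejection would be 0.18×0.10 + 0.82×0.025 = 3.9% to 0.18×0.15 + 0.82×0.025 = 4.8%. At 2.5% in each arm the effect is negligible. The trigger becomes likely only with a large true imbalance. It is also unsettled whether the permutation test would be the deciding test, because 14.1.1 names an ANCOVA. The documents do not support a claim that Estimand 2 must be dropped.

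**What to change.** Before unmasking, amend the SAP:

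- **4.1.2:** state that Estimand 2 uses a composite strategy, name the tail that completes the trimmed fraction, and give the summary as the difference in trimmed means. Record in section 18 that this replaces the protocol's hypothetical label and mean-change summary.
- **4.1.1 and 9.5:** add the matching hypothesis, and limit a rejection under Estimand 2 to that composite claim.
- **21:** delete the rule that suppresses Estimand 1 tables when Estimand 2 is primary. Report the Estimand 1 mean difference and the discontinuation rates beside the trimmed result, as protocol 11.4.4 planned for Estimand 1.
- **4.1.2 and 14.1.1:** say which test decides under Estimand 2, the permutation test or the ANCOVA.

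The cost is SAP wording and a few extra tables; no patients or data are needed. The sponsor gives up the ability to read an Estimand 2 rejection as a staining-only result. Making Estimand 1 primary in all cases, with trimmed means as sensitivity, is an option for the sponsor and not a required correction. Its price is that discontinuation itself would no longer count as a bad outcome in the primary test.

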8.1.4 Procedures for Final Study Entry

Patients must meet all inclusion and none of the exclusion criteria.

8.1.5 Methods for Assignment to Treatment Groups:

At Visit 1, patients who provide written informed consent will be assigned a unique 5-digit screening number, which includes the 2-digit site number plus a unique 3-digit screening number beginning with 001 (eg, 11-001, 11-002, 11-003, etc.). Screening numbers must be assigned in ascending consecutive order.

Prior to Visit 2, the Medical Monitor will review the medical and medication history, screening results and screening eligibility criteria for each patient who enters the run-in period, and confirm the patient's eligibility for the study. If there is a change in medical or medication status between Visits 1 and 2, the Medical Monitor will review and confirm the patient's eligibility for the study prior to randomization at Visit 2 (if possible) or as soon as possible after Visit 2.

At Visit 2, a patient who meets all the eligibility criteria will be randomized to receive treatment with 0.3% SI-614 or placebo in a 1:1 ratio. The Interactive Voice/Web Response System (IVRS/IWRS) will be used to account for the stratification factors.

Patient's will be stratified by the following factors and cut-offs:

1. Average of dryness and ocular discomfort at bedtime assessment for Run-in patient daily diary mean (Day -7 through Day -1).
 - a. ≤ 2.5
 - b. > 2.5
2. Change [REDACTED] in total corneal fluorescein staining at Visit 2
 - a. ≤ 3.5
 - b. > 3.5

Both strata will be entered into the IVRS/IWRS, which will assign the randomization number and the assigned kit number for the patient. The site staff will dispense to the patient the study kit labeled with the corresponding kit number. Both the randomization number and the dispensed study drug kit number will be recorded on the patient's source document and eCRF.

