As supportive analyses, two-sample t-tests and a Wilcoxon rank sum test will be conducted to compare the change from baseline [REDACTED] at Day 29 [REDACTED] between the two treatment groups. Additional exploratory comparisons of the mean raw scores of corneal total fluorescein staining score at Day 29 [REDACTED] and baseline [REDACTED] (Visit 2, Day 1) between the treatment groups will be conducted using two-sample t-tests and Wilcoxon rank sum tests. Quantitative summary statistics will be provided for baseline Day 1 [REDACTED] Day 29 [REDACTED] and change from baseline [REDACTED] at Day 29 [REDACTED].

Least Squares (LS) means with standard errors (SEs) for each treatment group and LS mean differences between treatment groups with SEs will be presented from the

ANCOVA model together with two-sided p-values and two-sided 95% confidence intervals. Sample means, sample mean differences with SEs, two-sided 95% confidence intervals, and two-sided p-values will be reported from the two-sample t-tests. Two-sided p-values will be reported from the Wilcoxon rank sum tests for observed data only analyses and LOCF analyses only. Trimmed means of each treatment group, trimmed mean differences between treatment groups, two-sided exact p-values and two-sided exact 95% confidence intervals will be presented from the permutation test with trimmed means.

Sensitivity analyses will include multiple imputation by placebo group-based PMM, multiple imputation via randomized treatment group-based MCMC, single imputation by LOCF, and analyses of observed data only using the ITT and PP populations.

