tCFS	Total Corneal Fluorescein Staining
TE-SAE	Treatment-Emergent Serious Adverse Event
TEAE	Treatment-Emergent Adverse Event
TFBUT	Tear Film Break-Up Time
TMF	Trial Master File
WHODrug	World Health Organization Drug Dictionary

1 Introduction

The purpose of this statistical analysis plan (SAP) is to describe the planned analyses and reporting in detail for the efficacy and safety assessments of study 614/1132 as well as relevant data collected in protocol 614/1132, Version 1.0 dated 23MAR2022.

This SAP is being written with due consideration of the recommendations outlined in the most recent International Conference on Harmonisation (ICH) E9 Guideline entitled Guidance for Industry: Statistical Principles for Clinical Trials, the most recent ICH E9 (R1) Guideline entitled Guidance for Industry: Statistical Principles for Clinical Trials: Addendum: Estimands and Sensitivity Analysis in Clinical Trials, and the most recent ICH E3 Guideline, entitled Guidance for Industry: Structure and Content of Clinical Study Reports.

The statistical analysis methods presented in this document will supersede the statistical analysis methods described in the clinical protocol. If additional analyses are required to supplement the planned analyses described in this SAP, they may be completed and will be identified in the clinical study report.

2 Study Objectives

The objective of this study is to evaluate the efficacy and safety of 0.3% SI-614 ophthalmic solution compared with placebo when administered 4 times daily (QID) for 84 days in patients with dry eye.

3 Study Design and Procedures

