3.1 General Study Design

This study is a Phase 3, multicenter, randomized, double-masked study to evaluate the efficacy and safety of 0.3% SI-614 Ophthalmic Solution compared to placebo in patients with dry eye. Approximately 230 patients will be randomized with a ratio of 1:1 into one of the two groups: (1) 0.3% SI-614, or (2) placebo, which they will be instructed to administer QID for 84 days. The randomization will be stratified by two factors:

- Average of dryness and ocular discomfort at bedtime assessment based on run-in patient daily diary mean from Day-7 through Day -1: ≤ 2.5 vs > 2.5
- Change [REDACTED] in total corneal fluorescein staining at Visit 2: ≤ 3.5 vs. > 3.5

Table 1 shows the scheduled study visits, their planned study day (note that there is no Day 0 and that Day 1 corresponds to the day of randomization), and the acceptable visit window for each study visit:

Table 1. Study Visit Windows

Scheduled Visit	Planned Study Day	Visit Window
Visit 1	Day -14	± 3 Days
Visit 2	Day 1	N/A
Visit 3	Day 8	± 2 Days
Visit 4	Day 15	± 2 Days
Telephone Visit 1	Day 22	± 2 Days
Visit 5	Day 29	± 3 Days
Telephone Visit 2	Day 43	± 2 Days
Visit 6	Day 57	± 3 Days
Telephone Visit 3	Day 71	± 2 Days
Visit 7	Day 85	± 3 Days

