14.1 Primary Efficacy Endpoint

14.1.1 PRIMARY ANALYSIS METHODS

Primary analysis of the CFB [REDACTED] to Day 29 [REDACTED] in tCFS will be performed using an Analysis of Covariance(ANCOVA) model adjusted for baseline value with treatment group as the explanatory variable on ITT population with Estimand 1 or ITT population with Estimand 2 depending on the rate of intercurrent events. Least squares (LS) means for each treatment group and the LS mean difference comparing 0.3% SI-614 with placebo will be presented from the model together with SEs, two-sided 95% CIs, and one-sided p-values.

Subject listings will be provided for the primary efficacy endpoint for all randomized patients.

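### SAP 4.1.2 leaves the Estimand 2 permutation test without a stated baseline adjustment or within-stratum permutation, and SAP 14.1.1 names a baseline-adjusted ANCOVA for the same estimand

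*SAP*

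**What the plan says.** SAP 4.1.2 makes Estimand 2 primary when Fisher's exact test on intercurrent events gives p<0.05 and the overall rate is above 5%. Patients who stop treatment for lack of efficacy or adverse events are trimmed, Table 2 sets the trimmed percentage, and "The permutation test will be used to test the treatment difference". Missing data from other discontinuations are imputed by MCMC within randomized arm. No covariate, strata or permutation scheme is named.

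SAP 14.1.1 bases the primary analysis on covariance adjustment. It describes a "model adjusted for baseline value with treatment group as the explanatory variable on ITT population with Estimand 1 or ITT population with Estimand 2". Results are reported with least squares means, two-sided intervals and one-sided p-values.

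Protocol 11.4.4 also analyses the fallback "using the permutation test with trimmed means methodology with Estimand 2" and adds that "two-sided exact p-values and two-sided exact 95% confidence intervals will be presented from the permutation test with trimmed means". Its baseline covariate belongs to the ANCOVA only. The SAP states that "The statistical analysis methods presented in this document will supersede the statistical analysis methods described in the clinical protocol".

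On allocation, SAP 3.1 says "The randomization will be stratified by two factors": the run-in bedtime symptom average (cut at 2.5) and the Visit 2 staining change (cut at 3.5). Protocol 8.1.5 says the IVRS/IWRS "will be used to account for the stratification factors". Five patients were randomized with wrong strata.

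**The concern.** Under Estimand 1 the primary comparison is adjusted for baseline staining. Under Estimand 2 the section that defines the test is silent on baseline, and the section that mentions baseline describes a different test. An analyst following 4.1.2 alone could shuffle labels freely on the raw change, and nothing in that section would rule it out.

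Two things follow from that choice. First, any precision that baseline offers is lost, in a setting where trimming may already have cost power. Second, a permutation p-value is exact only when the re-drawn allocations are ones the design could have produced. A free shuffle ignores the four strata, so its reference distribution is too wide when a stratum predicts outcome.

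The secondary endpoint is tested only if this test succeeds (SAP 9.5). Leaving the statistic open also leaves room for a choice after unmasking.

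**Working it through.** **1. The plan's own figure.** Inputs from Protocol 11.3: difference −0.75, SD 1.7, two-sided 0.05, power 90%.

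n per arm = 2 × (1.960 + 1.282)² × 1.7² / 0.75² ≈ 108 by the normal formula; the t-test version gives 108.94, so 109. Then 109 / 0.95 = 114.7, so 115. The stated 109 and 115 reproduce. The calculation is unadjusted, so the planned 90% does not rely on baseline.

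**2. What baseline is worth without trimming.** Adjusted SD = 1.7 × √(1 − ρ²), where ρ is the correlation of baseline with the Day 29 change. The documents do not give ρ. Power at 109 per arm:

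| ρ | SD | Power |
|---|---|---|
| 0 | 1.700 | 90.3% |
| 0.3 | 1.622 | 92.7% |
| 0.5 | 1.472 | 96.4% |
| 0.6 | 1.360 | 98.3% |

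**3. Smallest triggering case.** More than 5% of 230 means more than 11.5, so at least 12 events. The least extreme split of 12 with Fisher p<0.05 is 10 against 2: p = 0.034, overall 12/230 = 5.2%, worse arm 10/115 = 8.7%. Table 2 then gives 10% trimming.

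**4. Power in that case.** Monte Carlo with about 115 per arm, difference −0.75, SD 1.7, normal outcomes, blocks of 4 in four strata, and 10 active and 2 placebo events. Event patients are ranked worst and the worst 10% of each arm is trimmed. The baseline-adjusted version uses residuals from a regression on baseline pooled over arms and fitted without treatment. Ranges are over repeated runs of 500 to 1,500 trials per cell (standard error about 1.3 to 2 points).

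| ρ | Raw change, free permutation | Baseline-adjusted, within strata |
|---|---|---|
| 0 | 53–54% | 52–54% |
| 0.3 | 55–56% | 60–64% |
| 0.5 | 56–58% | 71–76% |
| 0.6 | 53–57% | 82–83% |

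The low starting level is mostly trimming. Keeping 103 of 115 removes 12 per arm; 10 of the 12 on active are event patients, against 2 of the 12 on placebo, so more of the worst observed scores leave the placebo arm.

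**5. Which part matters.** With event rates of 9% active and 2% placebo at ρ = 0.5, power is 56% raw and free, 59% raw within strata, 71% adjusted and free, and 70% adjusted within strata. In the 10-against-2 case, adjusted free against adjusted within strata gave 65% and 64% (ρ 0.3), 70% and 71% (0.5), and 81% and 83% (0.6). Baseline does nearly all the work; strata add little once baseline is in.

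**6. Direction.** With the imbalance reversed (2% active, 9% placebo, ρ = 0.5), power is 97% against 98%. The loss matters when events fall mainly on active.

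**7. Type I error.** With 7% events in both arms, the raw, free test rejected in 1.6–2.1% of null trials at one-sided 2.5% (standard error about 0.5 points). It errs towards conservatism.

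**The case against.** The strongest reply is that neither document says the test is raw or unrestricted. A reader might infer that the plan drops baseline under Estimand 2. The text does not support that: 4.1.2 is silent, 14.1.1 names a baseline-adjusted model for this estimand, and the protocol defines the method by a citation that cannot be consulted here. This stands, and the finding is therefore one of missing specification and conflict. The Estimand 2 line "Subjects who were mis-randomized will be analyzed as randomized using the correct baseline information" does not close the gap: it concerns five patients and puts no covariate into the test.

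A reader might also infer that the SAP promises an exact p-value. It does not; that wording is in Protocol 11.4.4, whose methods the SAP supersedes. The SAP does not, however, say what inference replaces it for this test.

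Omitting strata is not peculiar to Estimand 2: the primary ANCOVA omits them too, and SAP 14.1.2 adds a strata-adjusted ANOVA as a sensitivity analysis under either estimand. That is fair, though a permutation test takes its reference distribution from the allocation, so the omission bears on it more directly.

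Finally, the fallback may rarely be used. With 115 per arm the trigger probability is 1.2% if the true event rate is 5% in both arms, 0.01% if it is 2%, and 11% if the rates are 7% and 3%. In the 28-day Phase 2/3 study of 240 patients, adverse events led to discontinuation of two, one per arm; lack-of-efficacy discontinuations are not given. This limits the expected loss. It does not remove the need to define a confirmatory test beforehand.

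**Conclusion.** The point holds as an unspecified and internally inconsistent primary test under Estimand 2. SAP 4.1.2 and 14.1.1 name different procedures, and the permutation test has no stated covariate, permutation scheme or rule for multiply imputed data.

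Running it on raw change with free permutation would cost, in the smallest triggering case with most events on active, nothing at ρ = 0, about 5 points of power at 0.3, roughly 17 at 0.5, and 25 to 29 at 0.6. Protocol 11.4.4's exact p-value and interval would also not match the stratified randomization. A reader might infer a false-positive risk; the simulations show none.

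These sizes rest on assumptions outside the documents: ρ, normal scores, block size 4, events unrelated to outcome, one-sided trimming of the worst scores, and how closely the staining stratifier tracks baseline. The likelihood of reaching Estimand 2 looks low unless event rates differ between arms.

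**What to change.** State the same test in SAP 4.1.2 and 14.1.1, and record the change in Section 18. Under Estimand 2:

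- The primary test is the permutation test on trimmed means of the Day 29 change adjusted for baseline tCFS, using residuals from a regression on baseline pooled over arms, fitted without treatment in patients not trimmed for an intercurrent event.
- Patients with trimmed intercurrent events keep the worst rank.
- Labels are permuted within the four strata as entered in the IWRS, including for the five mis-stratified patients, because those entries generated the allocation.
- The p-value is one-sided at 0.025, in line with SAP 4.1.1.
- The rule for combining results over the MCMC imputations is given. Because imputation is by randomized arm, imputed values depend on the actual label, so the p-value should not be called exact without qualification when such values are present.
- The baseline-adjusted ANCOVA in 14.1.1 is confined to Estimand 1, or given a stated supportive role under Estimand 2.

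The cost is a short paragraph and some programming, settled before unmasking, with no new data. The small downside is that the estimate becomes a baseline-adjusted trimmed-mean difference, so the unadjusted trimmed means should be shown beside it.
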